## **1. Administrative Information**

### **1.1. Title**

Harnessing male peer networks to enhance engagement with HIV prevention: A large-scale cluster randomized trial to increase HIV self-testing and PrEP uptake among men in Eastern Zimbabwe.

### **1.2. Trial Registration**

The trial will be registered with ClinicalTrials.gov and the Pan African Clinical Trials Registry.

### **1.3. Protocol Version**

Version 2.2

### **1.4. Funding**

The study will be funded through the United States National Institute of Health through National Institute of Mental Health.

### **1.5. Sponsor**

The Stellenbosch University will be the sponsor for this study. Stellenbosch University has a Clinical trial insurance policy in place that provides cover in the event that a participant holds Stellenbosch University liable for any injuries or illnesses sustained during a trial.

## 2. Introduction

### 2.1. Background and Rationale

#### 2.1.1. Summary

The objective of this project is to use an implementation science approach to establish the impact of HIVST distribution through male social networks, with phone-based support and improved risk perception, on PrEP uptake among men in Eastern Zimbabwe. The project will leverage infrastructure and data associated with 20-year programme of HIV surveillance and behavioural research in a well-characterized population cohort hosted by the Manicaland Centre for Public Health Research, Zimbabwe. The project is particularly opportune given the very recent adoption of PrEP as a key component of the Zimbabwean national AIDS response and the subsequent roll-out of PrEP in all local clinics.

The study will utilise a cluster randomised design. In intervention clusters we will identify initial distributors who will receive an HIVST kit for personal use and HIVST kits to distribute to local peers. These peers can subsequently become distributors, allowing the intervention to propagate through peer networks. A toll-free helpline will provide pre- and post-test support and an SMS-based risk assessment will expedite PrEP initiation at the clinic. We will conduct a process evaluation of the intervention to assess implementation fidelity and causal mechanisms underlying trial effectiveness including how characteristics of peer networks affect outcomes. We will use the results of the study to quantify the population level impacts

and cost-effectiveness of male peer to peer HIVST distribution strategies on the uptake of PrEP in HIV hyper-endemic settings using a fully calibrated individual-based mathematical model. The envisaged long-term impact of this research is the development of a generalizable, multicomponent male peer based HIVST and PrEP uptake model for settings where HIV incidence is high.

The study protocol follows the Standard Protocol Items: Recommendations for Intervention Trials (SPIRIT). [1–3]

### **2.1.2. Background**

Effectively engaging men in HIV prevention remains one of the greatest challenges to driving the epidemic to low levels of endemicity in Sub Saharan Africa (SSA). [4–6] If HIV elimination strategies are to succeed in SSA, innovative solutions are needed to more effectively engage men in HIV testing, prevention and care.[7] Suboptimal engagement with HIV prevention by men increases their risk of HIV acquisition,[8] and is an important driver of new HIV infections in women.[9] Increased HIV testing is a prerequisite for meeting targets at subsequent stages in the HIV treatment and prevention cascades,[10, 11] but males face multiple gender-specific barriers to engagement with facility-based HIV testing and care services.[12] HIV self-testing (HIVST) addresses several key facility-based access barriers[13] and the distribution of HIVST through male peer networks to promote HIV prevention is feasible, acceptable and effective in SSA.[14, 15] Leveraging peer networks increases the penetration of health interventions to hard-to-reach individuals. [16] In hyperendemic settings in SSA the high HIV incidence in subgroups of the general population indicate that a population-wide scale-up of Pre Exposure Prophylaxis (PrEP) could substantially impact the HIV epidemic's trajectory.[17, 18] Demand for PrEP among men is high[19] and the use of HIVST in conjunction with PrEP increases adherence.[20] The positive impact of eHealth interventions on HIV care engagement has also been widely demonstrated.[21] Whilst support from male peers improves testing behaviour, no study yet has been able to measure the impact of such a strategy on the uptake of PrEP at scale.

This study will employ a combination of technologies and strategies that have been proven to work in isolation to overcome barriers to male engagement with care. [22–27] HIV Self testing (HIVST) which allows men to test privately and to retain autonomy in their engagement with healthcare have been shown to be acceptable to men. [14] HIVST has been adopted as part of the national HIV care strategy in many SSA settings including Zimbabwe. A meta-analysis of studies in Malawi, Zambia and Zimbabwe investigating the impact of community based HIVST distribution on ART initiation showed positive effects on levels of ART initiation and emphasised the importance of integrating initiation support with HIVST distribution.[23] Studies in Uganda showed that encouragement from a trusted peer increased the willingness of men to test.[24] Recent studies in both rural and urban SSA settings have shown that the peer distribution of HIVST to men is both feasible and acceptable. [22, 25] A recent review confirmed the advantages of peer distribution for males and emphasised the importance of combining distribution with linkage to existing provision for confirmatory testing, linkage to care and PrEP where it was available. A study conducted in KwaZulu Natal South Africa showed that HIVST distribution could reach to extended levels in a peer network and increase the take-up of HIV testing. [28] Research in Eswatini showed that demand for PrEP among men was high with a preference for PrEP delivery to be linked to testing or outpatient settings.[19] A systematic review has shown that use of mobile phone-based approaches can be effective in promoting behaviour change with trials showing improvement in adherence to ART and biological outcomes with results dependent on the precise strategy employed. [27]

HIV prevention cascades (HPCs) have been developed as a tool to track and increase availability, uptake and adherence to efficacious HIV prevention strategies.[29–31] This follows from the success of the HIV treatment cascade in articulating the multiple steps required to fully exploit the potential of ART. [30] These start by considering the fraction of the population who are at risk, and then apply filters that reflect the proportions for whom a service is available, that take up that service, that adhere to the use of the service, and that ultimately benefit from it. In this way, missed opportunities to maximize the impact of a particular 'prevention technology' are quantified. In this proposal, we consider the factors acting at individual, partner, community, and structural levels that influence and impede progression through HPCs for men with an ultimate focus on PrEP uptake. Using this overarching formulation, we have developed an intervention which targets multiple barriers to successful male engagement with HIV prevention. A prevention cascade (Fig 1) when applied in this setting to assess barriers to the adoption of PrEP amongst HIV negative men indicated low levels of knowledge and risk perception and extremely limited current access to the technology amongst this group (Fig 1). Whilst HIVST is a key component of the Zimbabwean Ministry of Health strategic response [32] our research indicates that whilst around 60% of men are aware of HIVST , less than 6% have actually used the kits.

[figure not shown]

Figure 1 An HIV Prevention Cascade for PrEP use populated with data from the 2021 Manicaland HIV surveillance survey

Process evaluations are central to both understanding what did and did not work during implementation of complex interventions, and for adjusting implementation in real-time to maximize effectiveness. [33] Past evaluations of randomised control trials at this site have stressed the importance of involving community members in programme design and implementation to optimise intervention outcomes. [34, 35] Previous work in this setting has highlighted the role formal and informal social networks play in affecting HIV risk acquisition[36, 37] and HIV care, [38, 39] suggesting that social networks are likely to affect the effectiveness of the proposed trial. A full understanding of the distribution networks within the trial is likely to provide vital insight into both where our trial did and did not work, and in what settings our model is likely to require additional adjustment. Exploration-phase work has shown that HIV prevention methods such as PrEP are wanted by men in this area, [40, 41] and that the various components proposed for our trial are feasible and likely to be of interest.

Our hypotheses are that: (i) pre-intervention context analysis will achieve a more acceptable implementation design that considers the array of distal and proximate determinants of

intervention outcomes; (ii) real-time feedback during implementation will facilitate adjustments to both the intervention and the evaluation; (iii) post-trial evaluation will identify “what works in which circumstances for whom” which is critical to assess fidelity and implementation quality; (iv) social networks, both in terms of individual position and community structure, will be important predictors of intervention effectiveness.

Our design for the process evaluation is guided by the updated Medical Research Council guidance for developing and evaluating complex interventions, [42] paying attention to broad context and stakeholder experiences before, during and after the intervention. It also fits within the Exploration Preparation Implementation Sustainment–(EPIS) framework,[43, 44] specifically focusing on the preparation and implementation phases, with an eye to building sustainment post-trial.

We have also scoped the complex context of PrEP delivery in Manicaland, identifying outer context components – including national and local government structures and existing NGOs supporting HIV prevention inner context components within our planned trial delivery system and the bridges between them. All of these will feed into our implementation plan.

Impact and cost-effectiveness are crucial considerations in deciding whether to adopt a new intervention. Mathematical modelling, combined with cost data collection, provides a widely used method to estimate population-level impact and cost-effectiveness, and to extrapolate estimates beyond the duration of the trial. The choice of mathematical model must include considerations of feasibility of approach (both in time to develop and calibrate the model, and availability of data to calibrate the model) and the ability to represent the epidemiology and proposed intervention as realistically as needed. Individual-based models (IBMs) offer a parsimonious and flexible way to characterize HIV prevention, where individuals have multiple prevention options and channels to use them. They also explicitly represent the sexual network, an advantage over other compartmental models. However until recently the computational intensive nature of IBMs, making systematic calibration challenging, [45] as well as the substantial data needs to parameterize the sexual network, means that IBMs have rarely been used in impact evaluation in practice.

## **2.2. Objectives**

The aims of the research are:

1. To establish the impact of HIVST distribution through peer networks with improved access and enhanced community support structures on the uptake of PrEP in men.
2. To conduct a process evaluation of the intervention in this typical rural African population and characterize peer networks.
3. To quantify the population level impacts and cost-effectiveness of male peer to peer HIVST distribution strategies on the uptake of PrEP in HIV hyper-endemic settings

## **2.3 Trial Design**

The study will use a cluster-randomised trial design with clusters based on existing village boundaries, which have been utilised as part of the ongoing population-based HIV surveillance. In some cases, neighbouring villages will be aggregated to give approximately equal numbers of adult men in each cluster. Feedback from the participatory ‘theory-of-change’ workshops involving key community stakeholders will be taken into account by the PI’s and CoI’s when considering further refinements that can support the successful implementation of the trial. Real-time feedback from the process evaluation will ensure the roll-out is as specified in the protocol thus maximising the fidelity of the intervention.

### **3. Methods, Participants, Interventions and Outcomes**

#### **3.1. Study Setting**

The study cohort from which participants will be recruited is located in Manicaland province, east Zimbabwe. [46] The most recent round of surveillance in 2018/19 was conducted across 8 sites ranging from rural to urban. [47] These sites represent the 5 of the major socioeconomic strata in Manicaland; small towns, agricultural estates, roadside settlements, subsistence farming areas and urban areas (Figure 6). Local healthcare is provided through a network of public sector primary care clinics, with clinics operating as public-private partnerships in the two estates.

#### **3.2 Eligibility Criteria**

All males aged 18 and over will be eligible for recruitment to the study.

#### **3.3 Interventions**

##### **3.3.1 Intervention – HIVST distribution through male peer networks**

The intervention will proceed with the following steps: (see summary Fig 2)

- i. Potential primary distributors will be identified by the research team following engagement with local key informants, these individuals will be contacted and screened for study enrolment. The desired characteristics of these individuals would be that they are respected members of their community with strong local networks of peers. If they choose to participate an informed consent procedure will be completed by the fieldworkers.
- ii. If enrolled, the distributor will be given a pack containing four HIVST kits, one for their own use and three for distribution within the cluster. The study team will collect basic demographic data (name/age / cell number) for the distributor and the intended recipients. They will also record the unique ID of the pack of kits. Advice will be provided on the correct use and interpretation of the HIVST, the need for post-test confirmatory testing in a health facility and the availability of HIV prevention methods including PrEP.
- iii. The distributor will be asked to give the test kits to the intended recipients within a seven-day period.
- iv. After seven days the helpdesk will contact the distributor and the intended recipients to ascertain whether kits have been received and used, to collect behavioural HIV risk data for the recipients and encourage attendance at a healthcare facility for a confirmatory test. HIVST recipients will be invited to complete the informed consent over the telephone and be enrolled in the study. Follow-up calls will be made to these individuals if necessary. Recipients will be encouraged to consider becoming distributors and advised on the location of community facilities (shops, pharmacies, hairdressers etc.) from where they can obtain the HIVST packs for distribution. This method of HIVST distribution through community-based hubs has been proven to be successful in studies in other Sub-Saharan African settings. [48] A small renumeration of \$1 per peer will be transferred electronically to the initial distributor for each kit successfully distributed. Successful distribution to peers is defined as the peer having received the HIVST and has been successfully contacted by the helpline to confirm receipt of the HIVST but does not have to use the HIVST or agree to enrol in the study as a distributor. Names and cell numbers will be collected for intended recipients by the study team and held confidentially.

- v. If the recipient chooses to become a distributor they will go to the facility and the owner will check using a real-time database that they have not already received a pack of kits for distribution. If they pass this screening, they will be given a pack of three HIVST kits for within cluster distribution, again A small renumeration will be paid to the facility owner for each pack of kits given out.
- vi. After seven days the helpdesk will contact the second level recipients and steps iv) and v) will be repeated until all kits allocated to a particular community have been distributed.
- vii. When participants attend a clinic for confirmatory testing, they will return the HIV test kit packaging with the unique label and based on their self-reported HIVST result (unreactive/reactive) be screened for PrEP or ART. The outcome of the screening will be recorded in a tick-box on the label and the packaging deposited in a secure box at the clinic from where it will be collected by the study team.
- viii. HIVST kits will be returned to the central data processing facility for data entry and an additional small renumeration of \$1 paid to the initial distributor for each individual attending the clinic and participating in a confirmatory HIV test.
- ix. All individuals initiating PrEP or ART will be contacted monthly for six months to provide support and to ascertain whether they are still adhering to/continuing with PrEP/ART.
- x. Additionally, we will contact all men who report they are still taking PrEP/ART at the end of the follow-up period in order to obtain a dry blood spot to verify the self-report of adherence. This will be sent for analysis in order to assess the intracellular levels of tenofovir diphosphate (TFV-DP) in red blood cells . [49]

In a second phase of the intervention, we will return to the intervention clusters and invite the initial distributors to participate in a second phase of wider distribution. In this stage they will be able to distribute the packs of kits to individuals they contact over the next 14 days resident anywhere within the study site. The distribution process will proceed as previously for up to 2 months following the initial acceptance of the HIVST pack.

[figure not shown]

Figure 2 Schematic flowchart for the intervention as described in steps i) to x) above

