### **3.3.6 HIVST packaging and kit inserts**

Study specific packaging will be created for each HIVST kit into which the original kit with packaging from the manufacturer will be inserted. A sticker on each box will contain the following information:

- A unique 6-digit identifier for the kit
- A set of tick-boxes on which the clinic staff will record the outcome of the engagement with the clinic
- A kit insert sheet within each box will contain the following:
  - A copy of the informed consent form
  - Details of accessing SMS-based HIV risk self-assessment tool
  - Contact details for the study helpline
  - Details of the study procedures including the renumerations paid for successful kit distribution and engagement of recipients with the primary care clinics

- Detailed instructions on the use and interpretation of the HIVST kit

Individual HIVST kits will be placed in a larger box with its own unique identifier. Four kits will be provided in these boxes for the primary distributors and three for the secondary distributors. The study team will keep a record of the unique identifiers of the kits packaged in each box to enable the kit distribution process to be tracked.

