## **3.4 Outcomes**

**The primary outcome** of the trial will be the proportion of men initiating PrEP out of all men aged 18 and over.

**Secondary outcomes will include:** i) the proportion of men self-testing for HIV over the period of the intervention out of all men aged 18 and over. and ii) the proportion of screened men adhering to PrEP or ART six months after initiation, measured by laboratory analysis of dry blood spots, out of all men initiating PrEP or ART after receiving an HIVST kit.

The qualitative performance evaluation will inform work to combine several quantitative data sources to evaluate how the intervention spread through social networks, and how network position and structure affected trial outcomes. We will combine information on intended and actual HIVST recipients with the existing Manicaland census data to measure what proportion of PrEP/ART eligible men were reached by our intervention. We will assess the level of network saturation achieved by the distribution process [16], and whether our approach reached individuals at higher risk of HIV acquisition as the recruitment process advanced – a key aim of the respondent driven sampling (RDS) methods on which our peer recruitment methods are based. Using entity resolution algorithms and hand-checking, we will identify linkages across distribution chains, and from this build network graphs of connections between men in the study areas. We will use these graphs to describe the structure of local male peer networks and statistically evaluate how characteristics of distributors and their social contacts influenced network distribution process and subsequent engagement with care. We will also evaluate whether intervention success differed across study clusters based on cluster-level network structures (e.g., density, clustering, age, and risk homophily) as well as by non-network characteristics (e.g., urbanicity, economy). Finally, once wider geographic distribution occurs in the second trial phase, we will evaluate whether distribution chains overlap and if greater geographical distribution affects study outcomes. We expect that our work will explain variation in outcomes and detail the contextual factors to consider when replicating or taking this intervention to scale. [33] We also expect to develop light-touch tools for use by implementors pre- and during implementation of such interventions, which can guide localization of this socially mediated design.

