### 3.6 Sample size

Based on data on HIV risk collected in the 2020/21 surveillance round we estimate that 33% of men aged 18 and over, will fulfil the requirement for PrEP initiation. A comparable study indicated that 43% of those identified as at risk would take-up PrEP. [18] In the 2020/21 surveillance round 3/3591 (0.14%) men were currently using PrEP. With a continued roll-out of PrEP until the start of the study, we assume a baseline PrEP usage of 1% which will increase to 2% over the course of the trial in control communities. The study will use a cluster-randomised trial design. To have sufficient men in each cluster to explore multiple waves of network recruitment we will create 22 clusters in the intervention arm and 22 in the control, from a total population of 3591 men which equates to 81 men in each cluster. The clusters will be created from either a single village or groups of neighbouring villages. In each intervention cluster a maximum of 90 HIVST kits will be distributed, assuming that 70% of these kits reach men in the cluster, 80% of these men use the HIVST, 33% of these are eligible for PrEP and 43% of these initiate PrEP, we estimate we will have 7.15 men / cluster initiating PrEP a total of 157 men. This represents 8.8% of the study population in the intervention clusters. Using an Intra-Cluster correlation coefficient of 0.1, a conservative estimate based on data collected in similar settings [58] and with a total sample size in the intervention and control arms of 3591 we will have greater than 85 % power to detect a difference in the percentage of men initiating PrEP from 2% in the control arm versus 8.8% in the intervention arm.

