### 3.7 Recruitment

The initial distributors will be identified by the research team as described above. We will have an initial target number of distributors e.g., 5 per intervention cluster. We will have target recruitment of 63 men in each cluster. If it becomes clear that the target recruitment for an individual cluster will not be reached, we will identify further initial distributors in the cluster and re-start the distribution process. We will provide telephone support for study participants to maximise adherence to PREP/ART and maintain retention in the study.

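### Phase 2 kits may go to men in control clusters, while the self-testing window appears to include phase 2 and the primary outcome has no closing point

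*Protocol*

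**What the plan says.** - **Distribution area (Protocol 3.3.1).** Phase 1 kits are for use inside the distributor's own cluster. The protocol then describes a second phase of the intervention, lasting up to two months, in which initial distributors may "distribute the packs of kits to individuals they contact over the next 14 days resident anywhere within the study site". No section bars residents of control clusters. Section 3.3.2 defines control only as the existing community health worker programme.
- **Primary outcome (3.4).** "the proportion of men initiating PrEP out of all men aged 18 and over", with no start or end date.
- **Secondary outcome (i) (3.4).** "the proportion of men self-testing for HIV over the period of the intervention out of all men aged 18 and over".
- **Phase 2 in 3.4.** It appears only in the paragraph on networks: "once wider geographic distribution occurs in the second trial phase, we will evaluate whether distribution chains overlap", together with an evaluation of its influence on study outcomes.
- **Sample size (3.6).** The intervention figure of 8.8% rests on within-cluster kits: "In each intervention cluster a maximum of 90 HIVST kits will be distributed". The control figure of 2% is usage reached over the duration of the trial.
- **Analysis and blinding (5.3, 4.2).** Analysis is by intention to treat according to the randomised cluster. Participants, study team and analysts are not blinded.

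**The concern.** The design permits intervention kits to reach control men during a stage that the protocol itself calls part of the intervention. The outcome definitions do not end before that stage. A self-test or PrEP initiation prompted by a phase 2 kit in a control village is then a control-arm event.

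This goes further than a detail left for an analysis plan. The self-testing window, followed as worded, most naturally takes in the contaminated months. For the primary outcome, the two halves of the sample size point to different horizons: within-cluster distribution for the intervention arm, the whole trial for the control arm. A cut-off settled after data have accrued, by analysts who know the allocation, would be open to challenge.

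**Working it through.** **1. Can phase 2 reach control men?** The term study site is not defined and arm by site is not shown, so this is an inference.
- Sections 3.1 and 3.6 give 8 sites and 44 clusters: 44/8 = 5.5 clusters per site.
- Section 4.1 stratifies allocation on five strata. If each site belongs to one stratum, at least two strata have a single site, because having at most one such stratum would need at least 1 + 4 × 2 = 9 sites. Stratified allocation should then place both arms in those sites.
- If the term means the whole study area, control clusters are included outright.

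**2. The plan's own figures.**
- Intervention: 90 × 0.70 × 0.80 × 0.33 × 0.43 = 7.15 men per cluster; × 22 = 157; 7.15/81 = 8.8%.
- Cluster size 3591/44 = 81.6; design effect 1 + 80.6 × 0.1 = 9.06; effective n per arm 1795.5/9.06 = 198.
- 2.0% v 8.8%, two-sided 5% level (assumed, as it is not stated), unpooled normal formula: power 85.7% (85.2% pooled). This agrees with the stated figure of more than 85%. It allows for no phase 2 kits in either arm.

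**3. Illustration of direction.** The protocol gives no phase 2 volume and no control share. Assumed inputs:
- First-wave kits only: 5 distributors (given in 3.7 only as an example) × 22 clusters × 3 kits = 330. Onward waves would add to this.
- 70% reach, borrowed from the within-cluster assumption: 231 men.
- 0.80 × 0.33 × 0.43 = 0.1135 initiations per man reached. Full gain if all were in one arm: 231 × 0.1135/1795.5 = 1.46 points.
- Control share s: control = 2.0% + s × 1.46 points; intervention = 8.8% + (1 − s) × f × 1.46 points.
- Model (a): f = 1. Model (b): only men without a phase 1 kit can gain. Section 3.7 says "We will have target recruitment of 63 men in each cluster", so f = 1 − 63/81.6 = 0.228.

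| Control share | Control | Ratio (a) | Power (a) | Ratio (b) | Power (b) |
|---|---|---|---|---|---|
| Plan, no phase 2 | 2.00% | 4.4 | 86% | 4.4 | 86% |
| 10% | 2.15% | 4.7 | 92% | 4.2 | 86% |
| 25% | 2.37% | 4.2 | 89% | 3.8 | 83% |
| 50% | 2.73% | 3.5 | 81% | 3.3 | 76% |
| 75% | 3.10% | 3.0 | 72% | 2.9 | 69% |

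The ratio falls below plan when s exceeds f/(f + 4.4): 18.5% in (a), 4.9% in (b), whatever the kit number. For 330 kits, power falls below plan above about 36% in (a) and 11% in (b).

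**4. Self-testing.** The plan's inputs give 63 × 0.80/81.6 = 62% in the intervention arm. Full phase 2 gain is 231 × 0.80/1795.5 = 10.3 points, so control shares of 10, 25, 50 and 75% add 1.0, 2.6, 5.1 and 7.7 points to the control rate. No control rate is stated. Section 2.1.2 reports that "less than 6% have actually used the kits", but that is survey use, not a rate under the control programme, so a planned ratio cannot be fixed.

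**The case against.** Outcome cut-offs are often set in an analysis plan, and the protocol hints at a phase 1 comparison. The intervention figure in 3.6 uses within-cluster kits, wider distribution is examined in the network paragraph of 3.4, and 3.8 lists it as a separate stage. These hints stand, but the outcome definitions do not adopt them, and the control figure of 2% points the other way.

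A reader might infer that no analysis plan could now exclude phase 2 from self-testing. The text does not go that far. The Figure 2 caption ties the intervention to steps i to x, and phase 2 is described after step x, so a narrower reading is open. The wording is ambiguous, and its plain reading includes phase 2.

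A reader might also infer a definite power loss. Holding the intervention arm at 8.8% and letting 10% or 20% of the 6.8-point effect reach controls gives control rates of 2.68% and 3.36% and power of about 75% and 63%. This is not supported. It ignores added uptake in the intervention arm, and it needs about 108 to 215 control men reached (0.0068 or 0.0136 × 1795.5/0.1135), which is 47% to 93% of the 231 assumed above.

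The scenario inputs are weak in any case. Model (b) treats men who hold an unused phase 1 kit as unable to gain. For self-testing, the plan's own inputs leave 38% of men untested rather than 23% without a kit, so (b) would overstate dilution there.

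**Conclusion.** The point holds as a defect in the outcome definitions and should be fixed. Phase 2 is open to control residents on the protocol's wording, the self-testing window includes it on a plain reading, the primary outcome has no end, and analysis by randomised cluster turns any spillover into control events. That sites contain both arms is a reasonable inference, not a stated fact.

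The size and direction of the net effect cannot be derived. In the illustration the PrEP ratio ranges from 4.7 down to 2.9 and power from 92% down to 69%, against 4.4 and 86% planned. Those figures rest on an assumed 330 kits and assumed control shares of 10% to 75%. They show that the estimate depends on the cut-off and do not predict a loss.

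It would also be too much to say that closing before phase 2 makes the outcome match the sample size in full. It matches the intervention figure; the control figure needs its own restatement.

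**What to change.** - **Section 3.4.** Define the primary outcome and self-testing over one fixed calendar window, the same for the intervention and control clusters of a site or stratum, closing no later than the first release of phase 2 kits there.
- **Phase 2 reporting.** Report phase 2 events separately by randomised arm, labelled as a comparison subject to contamination. Count the phase 2 kits reaching each arm. Section 3.3.6 supports this ("The study team will keep a record of the unique identifiers of the kits packaged in each box"), as do the recipient details recorded under 3.3.1.
- **Section 3.6.** State the 2% control assumption over the same window.

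The cost is protocol wording; phase 2 itself need not change. There are three downsides. PrEP initiations that lag behind late phase 1 kits would not be counted. If phase 1 is staggered within a site (the timeline bars are not readable here), late clusters have a shorter window or phase 2 starts later there. The control assumption, and with it the power statement, may need to be revised.
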